5. ENDPOINTS

5.1 PRIMARY ENDPOINT

Section 5.2.1 of the CTP: *Primary endpoint to assess safety and tolerability of BI 473494 is the number [N (%)] of subjects with drug-related adverse events.*

5.2 SECONDARY ENDPOINTS

5.2.1 Key secondary endpoints

This section is not applicable as no key secondary endpoints have been defined in the CTP.

5.2.2 Secondary endpoints

Section 5.5.1.1 of the CTP: *The following pharmacokinetic parameters will be determined for BI 473494 if feasible:*

- *AUC_{0-tz} (area under the concentration-time curve of the analyte in plasma over the time interval from 0 to the last quantifiable data point)*
- *C_{max} (maximum measured concentration of the analyte in plasma)*

6. GENERAL ANALYSIS DEFINITIONS

6.1 TREATMENTS

It was planned that in total 88 healthy male subjects participate in the trial, according to 11 sequential groups comprising 8 subjects per group (6 on active drug and 2 on placebo).

For details of dosage and formulation see Table 6.1: 1 below.

Table 6.1: 1 Labels for treatments for use in the CTR

Treatment	Short label
P* Placebo solution, sc, qd	Placebo
A BI 473494, solution for injection, 35 ug	BI 35 ug
B BI 473494, solution for injection, 75 ug	BI 75 ug
C BI 473494, solution for injection, 150 ug	BI 150 ug
D BI 473494, solution for injection, 300 ug	BI 300 ug
E BI 473494, solution for injection, 550 ug	BI 550 ug
F BI 473494, solution for injection, 1.0 mg	BI 1.0 mg
G BI 473494, solution for injection, 1.6 mg	BI 1.6 mg
H BI 473494, solution for injection, 2.6 mg	BI 2.6 mg
I BI 473494, solution for injection, 4.0 mg	BI 4.0 mg
J BI 473494, solution for injection, 6.0 mg	BI 6.0 mg
K BI 473494, solution for injection, 8.5 mg	BI 8.5 mg

*: The placebo control group in the safety evaluation will consist of all placebo treated subjects, regardless of the dose group in which they were treated.

Dose escalation was stopped after the second dose group (Treatment B / 75µg BI 473494). Therefore, all analyses will be performed for the first and second dose group only (treatments Placebo, 35µg BI 473494 and 75µg BI 473494).

The following separate study phases will be defined for the analyses of AEs:

- **Screening** (ranging from 0:00 h on day of informed consent until administration time of study drug (BI 473494 or Placebo))
- **On treatment**
 - **BI 473494/Placebo treatment** (separately for each treatment, ranging from the time of administration of BI 473494 / Placebo until 0:00h on the day after trial termination date)

Please note that all AEs reported between start of trial drug administration and the last per-protocol contact will be considered on treatment (i.e. no follow-up period is considered in this trial).

Displays of AEs will be presented separately for the treatments Placebo, 35µg BI 473494 and 75µg BI 473494.

Two types of AE displays will be provided in the report:

A) Section 15.3 and Appendix 16.1.13.1.8 (for ClinicalTrials.gov and EudraCT only) of the CTR displays:

In these displays, the on treatment phase will be analysed (labelled with the name of the study treatment (short label)). Screening will not be included in this analysis.

The following total will be provided in addition (Section 15.3 only):

- a total over all BI 473494 treated phases ("**BI Total**")
- a total over all on treatment phases included in this analysis ("**Total on treatment**") (Section 15.3 only)

B) Section 15.4 and Appendix 16.1.13.1.8 (except for ClinicalTrials.gov and EudraCT) of the CTR displays:

- Screening
- On treatment (labelled with the name of the study treatment (short label))

In Section 16.1.13.1.8 AE tables, the following totals will be provided in addition:

- a total over all BI 473494 treated phases ("**BI Total**")
- a total over all study phases ("**Total**")

Tables of vital signs and laboratory values will present results by the above mentioned on treatment phase.

For detailed information on the handling of the treatments in the O*C views refer to Technical TSAP ADS (analysis data set) plan and Analysis Data Reviewers guide.

6.2 IMPORTANT PROTOCOL DEVIATIONS

Data discrepancies and deviations from the CTP will be identified for all treated subjects.

Consistency check listings (for identification of deviations of time windows) and a list of protocol deviations (e.g. deviations in drug administration, in blood sampling times, etc.) will be provided to be discussed at the Report Planning Meeting and database lock meeting (RPM/DBLM). At this meeting, all manual deviations identified at the sites by the CRAs and deviations too complex to program will be reviewed by the trial team to decide which are considered important. For definition of important protocol deviations (iPD), and for the process of identification of these, refer to the Boehringer Ingelheim (BI) SOP "Identify and Manage Important Protocol Deviations (iPD)" ([2](#)).

If any iPDs are identified, they are to be summarised into categories and will be captured in the RPM/DBLM minutes via an accompanying Excel spreadsheet ([3](#)). The following [Table 6.2.1](#) contains the categories which are considered to be iPDs in this trial. If the data show other iPDs, this table will be supplemented accordingly by the time of the RPM/DBLM at the latest.

The iPDs will be summarised and listed.

Table 6.2: 1 Important protocol deviations

Category /Code		Description
A		Entrance criteria not met
	A1	Inclusion criteria violated
	A2	Exclusion criteria violated
B		Informed consent
	B1	Informed consent not available
	B2	Informed consent too late
C		Trial medication and randomisation
	C1	Incorrect trial medication taken
	C2	Randomisation not followed
	C3	Non-compliance
D		Concomitant medication
	D1	Concomitant medication with the potential to affect the assessment of the trial medication
E		Missing data
	E1	Certain deviations from procedures used to measure secondary data
F		Incorrect timing¹
	F1	Certain deviations from time schedule used to measure secondary data
G		Other trial specific important deviations
	G1	Appropriate fasting condition not met prior to study drug administration
	G2	Protocol deviations affecting safety and rights

¹ Time deviations will only be flagged as iPd, when leading to exclusion of the entire subject from an analysis set

6.3 SUBJECT SETS ANALYSED

- Treated set (TS):

This subject set includes all subjects who were dispensed study medication and were documented to have taken at least one dose of investigational treatment.

This is the full analysis set population in the sense of ICH-E9 (1).

It is used for demographics, baseline characteristics, and safety analyses.

The ECG analyses are performed on the TS.

Section 7.3.2 of the CTP: *Pharmacokinetic parameters of a subject will be included in the analysis unless the subject has an important protocol deviation relevant for the evaluation. Whether a protocol deviation is important will be decided no later than in the Report Planning Meeting.*

Reasons for exclusion of single pharmacokinetic parameters may be:

- *The subject experiences emesis at or before two times median t_{max} . Median t_{max} is to be determined for the test product excluding the subjects experiencing emesis.*
- *The subject experiences emesis at any time during the labelled dosing interval.*
- *Time deviations*
- *Use of restricted medications*

The subject set for the evaluation of PK endpoints [...] will include all treated subjects that provide at least one observation for at least one secondary endpoint without important protocol deviations with respect to the statistical evaluation of PK endpoints.

- PK parameter analysis set (PKS):

The PK parameter analysis set (PKS) includes all subjects from the TS receiving BI 473494 who provide at least one secondary PK parameter that was not excluded according to the description above.

Section 7.3.2 of the CTP: *It will be decided in the Report Planning Meeting which subjects are to be included in the PKS.*

Excluded subjects will be listed with their individual plasma concentrations and individual pharmacokinetic parameters, however, will not be included in descriptive statistics for plasma concentrations, pharmacokinetic parameters or other statistical assessment.

The descriptive analysis of PK concentrations will be based on the analysis data set (ADS) ADPC as described at the beginning of [Section 7](#).

Table 6.3: 1 Analysis sets for endpoints/data description

Endpoint/data description	Analysis set		
	TS	PKS	PDS
Primary and further safety endpoints (incl. ECG)	X		
Secondary		X	
PK endpoints			X
Demographic/baseline data	X		
Important protocol deviations	X		
Disposition	X		

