Main criteria for inclusion: Healthy male subjects, age of 18 to 45 years (inclusive), body mass index (BMI) of 20.0 to 29.9 kg/m ² (inclusive)				
Test products: BI 473494 solution for injection (1 mg/mL and 10 mg/mL) dose: 35 µg - 75 µg - 150 µg - 300 µg - 550 µg - 1.0 mg - 1.6 mg - 2.6 mg - 4.0 mg - 6.0 mg - 8.5 mg mode of admin.: Subcutaneous (SC) injection				
Comparator product: Placebo (isotonic sodium chloride solution) dose: Not applicable mode of admin.: SC injection				
Duration of treatment: Single dose				

Proprietary confidential information © 2017 Boehringer Ingelheim International GmbH or one or more of its affiliated companies

Name of company: Boehringer Ingelheim		Tabulated Trial Protocol		
Name of finished product: Not applicable				
Name of active ingredient: BI 473494				
Protocol date: 02 May 2017	Trial number: 1400-0001		Revision date: Not applicable	
Criteria for safety: Primary endpoint to assess safety and tolerability of BI 473494 is the number [N (%)] of subjects with drug-related adverse events (AEs). Further criteria of interest: 
• AEs including clinically relevant findings from the physical examination, safety laboratory tests, 12-lead electrocardiogram (ECG), vital signs (blood pressure [BP], pulse rate [PR])				
Criteria for pharmacokinetics: Secondary endpoints: AUC _{0-tz} and C _{max} of BI 473494				
Criteria for pharmacodynamics:				
Statistical methods: Descriptive statistics will be calculated for all endpoints. Dose proportionality of BI 473494 will be explored using a regression model. A 95% confidence interval (CI) for the slope will be computed.				

Proprietary confidential information © 2017 Boehringer Ingelheim International GmbH or one or more of its affiliated companies

FLOW CHART

Visit	Day	Planned time (relative to trial activities ¹⁷ [h:min])	Approximate clock time of actual day [h:min]	Event and comment	Safety laboratory	PK _{urine} ^{10,12,13}	12-lead ECG	Vital signs (BP, PR)	Questioning for AEs and concomitant therapy ⁶
1	-21 to -2			Screening (SCR) ¹	x				
2	-1	-24:00	08:00	Ambulatory visit ⁷	x ⁷		x	x	x
		-12:30	18:30	Admission to trial site	x ¹⁵		x ⁷	x ⁷	x
		-12:00	19:00	Dinner					
	1	-0:45 ²	06:15	Allocation to subject number				x	x
		-0:10	06:50						
		0:00*	07:00						
		0:15	07:15						
		0:30	07:30						
		0:45	07:45						
		1:00	08:00					x	x
		1:30	08:30					x	x
		2:00	09:00	240 mL fluid intake					
		3:00	10:00						

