8.2 DATA QUALITY ASSURANCE	80
8.3 RECORDS	81
8.3.1 Source documents	81
8.3.2 Direct access to source data and documents	81
8.3.3 Storage period of records	81
8.4 EXPEDITED REPORTING OF ADVERSE EVENTS	81
8.5 STATEMENT OF CONFIDENTIALITY	81
8.6 COMPLETION OF TRIAL	82
9. REFERENCES	83
9.1 PUBLISHED REFERENCES	83
9.2 UNPUBLISHED REFERENCES	85
10. APPENDICES	86
11. DESCRIPTION OF GLOBAL AMENDMENT(S)	87

ABBREVIATIONS

ADA	Anti-drug antibody
AE	Adverse event
AESI	Adverse events of special interest
$Ae_{t_1-t_2}$	Amount of analyte eliminated in urine over the time interval t_1 to t_2
AMP	Auxiliary Medicinal Product
ANCOVA	Analysis of covariance
ANOVA	Analysis of variance

AUC_{0-tz} Area under the concentration-time curve of the analyte in plasma over the time interval from 0 to the last quantifiable data point

β	Slope parameter associated with the power model used to evaluate dose proportionality
BI	Boehringer Ingelheim
BLQ	Below limit of quantification
BMI	Body mass index (weight divided by height squared)
BP	Blood pressure
BW	Body weight
CA	Competent authority
CALCR	Calcitonin receptor
CI	Confidence interval

C_{\max} Maximum measured concentration of the analyte in plasma

CML Clinical Monitor Local

Proprietary confidential information © 2017 Boehringer Ingelheim International GmbH or one or more of its affiliated companies

CRA	Clinical Research Associate
CRF	Case report form
CTP	Clinical trial protocol
CTR	Clinical trial report
CTSU	Clinical Trial Supplies Unit
CYP	Cytochrome P450
DG	Dose group
DI	Disposition index
DILI	Drug induced liver injury
EC ₅₀	Half-maximal effective concentration
ECG	Electrocardiogram
EDTA	Ethylenediaminetetraacetic acid
EMA	European Medicines Agency
EOT	End of trial
F	Absolute bioavailability factor
FDA	Food and Drug Administration
FE	Fluoride EDTA
FIH	First in human
GCP	Good clinical practice
GLP	Good laboratory practice
HbA1c	Glycosylated Haemoglobin A1c (N-(1-Deoxy)Fructosyl-Haemoglobin)
HED	Human equivalent dose
HR	Heart rate
IB	Investigator's brochure
IEC	Independent Ethics Committee
IPVs	Important protocol violations
IRB	Institutional Review Board
ISF	Investigator site file

LC-MS/MS Liquid chromatography with tandem mass spectrometry
MedDRA Medical Dictionary for Regulatory Activities

NOA	Not analysed
NOAEL	No observed adverse effect level
NOP	No peak detectable
NOR	No valid result
NOS	No sample available
PD	Pharmacodynamic(s)
PE	Polyethylene
PK	Pharmacokinetic(s)
PKS	Pharmacokinetic set
PP	Polypropylene
PR	Pulse rate

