4.1.5 Drug assignment and administration of doses for each subject

The treatments to be evaluated are outlined in [Table 4.1.5: 1](#) below. The dose volume for placebo corresponds to the dose volume of the respective dose level.

Table 4.1.5: 1 BI 473494 and placebo treatments, SC administration

Dose group	Substance	Pharmaceutical form	Unit strength	Dose volume per administration (single dose)	Total dose
1	BI 473494	Solution for injection	1 mg/mL	35 µl = 0.035 mL	35 µg
2	BI 473494	Solution for injection	1 mg/mL	75 µl = 0.075 mL	75 µg
3	BI 473494	Solution for injection	1 mg/mL	150 µl = 0.15 mL	150 µg
4	BI 473494	Solution for injection	1 mg/mL	300 µl = 0.3 mL	300 µg
5	BI 473494	Solution for injection	1 mg/mL	550 µl = 0.55 mL	550 µg
6	BI 473494	Solution for injection	1 mg/mL	1000 µl = 1.0 mL	1.0 mg
7	BI 473494	Solution for injection	10 mg/mL	160 µl = 0.16 mL	1.6 mg
8	BI 473494	Solution for injection	10 mg/mL	260 µl = 0.26 mL	2.6 mg
9	BI 473494	Solution for injection	10 mg/mL	400 µl = 0.4 mL	4.0 mg
10	BI 473494	Solution for injection	10 mg/mL	600 µl = 0.6 mL	6.0 mg
11	BI 473494	Solution for injection	10 mg/mL	850 µl = 0.85 mL	8.5 mg
1-11	Placebo*	Solution for injection	--	identical to active treatment	--

* Subjects receiving placebo are equally distributed across dose groups

The syringes containing the SC solutions for administration (BI 473494 or placebo) will be prepared by pharmacists, qualified pharmacy staff members or qualified medical study personnel at the trial site under the responsibility of the Investigator. The Investigator can decide at any time to stop dosing or (after consultation with the Sponsor) to decrease the dose escalation by adding intermediate doses in case of intolerance or safety concerns.

The trial medication BI 473494 or placebo will be administered to subjects on Day 1 of Visit 3 (at time-point 0:00) by SC injection into a lifted skin fold of the abdominal wall by the investigating physician or an authorised designee while subject lies in semi-upright position. Skin is sanitized prior to injection. Size of syringes used for administration is dependent on administered volume (e.g. BD Micro-Fine™ + Demi 0.3 mL with 8 mm needle attached or

Proprietary confidential information © 2017 Boehringer Ingelheim International GmbH or one or more of its affiliated companies

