4.3 TREATMENT COMPLIANCE

Compliance will be assured by administration of all trial medication in the study centre under supervision of the investigating physician or a designee. The measured plasma concentrations of investigational and non-investigational medicinal products and urinary excretion of BI 473494 will provide additional confirmation of compliance.

Subjects who are non-compliant (for instance, who do not appear for scheduled visits or violate trial restrictions) may be removed from the trial and the CRF will be completed accordingly (for further procedures, please see [Section 3.3.4.1](#)).

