7.3.2 Secondary analyses

The secondary parameters (refer to [Section 5.5.1](#)) will be calculated according to the BI Standard Operating Procedure (SOP) ‘Standards and processes for analyses performed within Clinical Pharmacokinetics/Pharmacodynamics’ ([001-MCS-36-472](#)).

Proprietary confidential information © 2017 Boehringer Ingelheim International GmbH or one or more of its affiliated companies

Pharmacokinetic parameters of a subject will be included in the analysis unless the subject has an important protocol violation relevant for the evaluation. Whether a protocol violation is important will be decided no later than in the Report Planning Meeting.

Reasons for exclusion of single pharmacokinetic parameters may be:

- The subject experiences emesis at or before two times median t_{max} . Median t_{max} is to be determined for the test product excluding the subjects experiencing emesis.
- The subject experiences emesis at any time during the labelled dosing interval.
- Time deviations
- Use of restricted medications

The subject set for the evaluation of PK endpoints (PKS) will include all treated subjects that provide at least one observation for at least one secondary endpoint without important protocol violations with respect to the statistical evaluation of PK endpoints. It will be decided in the Report Planning Meeting which subjects are to be included in the PKS.

Excluded subjects will be listed with their individual plasma concentrations and individual pharmacokinetic parameters, however, will not be included in descriptive statistics for plasma concentrations, pharmacokinetic parameters or other statistical assessment.

Assessment of dose proportionality

Dose proportionality will be assessed using the pharmacokinetic endpoints as specified in [Section 5.5.1.1](#).

The basic model for the investigation of dose proportionality will be a power model that describes the functional relationship between the dose and PK endpoints.

$$\exp(Y_{ij}) = \alpha' * \exp(X_i)^\beta * \varepsilon'_{ij}$$

The model consists of a regression model applied to log-transformed data. The corresponding ANCOVA model includes the logarithm of the dose as a covariate.

Together with $\alpha' = \exp(\alpha)$ and $\varepsilon'_{ij} = \exp(\varepsilon_{ij})$, taking natural logarithms converts this model to a linear form as follows:

$$Y_{ij} = \alpha + \beta * X_i + \varepsilon_{ij}$$

where

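### SAP 6.3 lets AUC0-tz and Cmax of BI 473494 be excluded for early vomiting, although the drug is a single subcutaneous injection that vomiting cannot remove

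*SAP*

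**What the plan says.** SAP 6.3 takes its exclusion list from Protocol 7.3.2. The list opens permissively: "Reasons for exclusion of single pharmacokinetic parameters may be". Two of its four items concern vomiting:

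- **First item:** "The subject experiences emesis at or before two times median" tmax. The reference value "is to be determined for the test product excluding the subjects experiencing emesis".
- **Second item:** "The subject experiences emesis at any time during the labelled dosing interval".

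The other two items are time deviations and restricted medications.

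SAP 6.3 then defines the PKS in its own words: treated subjects who received BI 473494 and still have at least one secondary PK parameter after the list has been applied. The secondary parameters are AUC0-tz and Cmax of BI 473494 (SAP 5.2.2 and SAP 4).

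The protocol synopsis gives the test product as BI 473494 solution for injection, "mode of admin.: Subcutaneous (SC) injection", as a single dose. Protocol 4.1.5 describes administration "by SC injection into a lifted skin fold of the abdominal wall".

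**The concern.** An emesis exclusion makes sense for an oral product, because a subject who vomits soon after dosing may lose part of the dose. A dose in the subcutaneous tissue of the abdominal wall cannot be lost that way, and no visible text gives another pharmacokinetic reason for the rule. A concentration profile from a subject who vomits is therefore a valid profile of the dose given.

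The two endpoints affected are the only secondary endpoints visible, and each is summarised from a handful of subjects. Vomiting is also foreseeable. Protocol 4.2.1 names it among the events that may occur as the dose rises, and Protocol 3.3.4.2 has stopping rules for it. The list leaves the decision to the Report Planning Meeting and gives no criterion for when vomiting should matter for an injected drug.

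**Working it through.** There is no planned figure to reproduce: Protocol 7.6 says that the sample size is not based on a power calculation. The check is therefore a reading of the text, followed by an illustration of size.

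**Does the list reach BI 473494?**

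1. The first item sets its window from the test product, which the synopsis identifies as BI 473494.
2. The PKS in SAP 6.3 is confined to subjects who received BI 473494, and membership depends on a secondary parameter surviving the list.
3. Those parameters are AUC0-tz and Cmax of BI 473494.

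So the first item applies to this analyte.

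**How long is the window?** Protocol 2.3 gives anticipated median tmax values of 16–20 h (from a related compound in humans) and 32–40 h (from monkeys).

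- 2 × 16–20 h = 32–40 h
- 2 × 32–40 h = 64–80 h

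The rule itself would use the trial's own median tmax, so these are only indications.

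**What does losing one value do?** Inputs are 6 active subjects per dose group (Protocol 3.1) and the geometric mean as a planned statistic (SAP 7). The documents give no PK variability, so CV = 30 / 40 / 50% is assumed.

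- Log-scale SD: σ = √ln(1 + CV²) = 0.294 / 0.385 / 0.472.
- Precision: the standard error of the log geometric mean is σ/√n. Going from 6 to 5 values multiplies it by √(6/5) = 1.095, a rise of 9.5% whatever the CV.
- Typical shift: the SD of (log mean of 5 − log mean of 6) is σ√(1/5 − 1/6) = 0.054 / 0.070 / 0.086. Back-transformed, this is about 5.5 / 7.3 / 9.0% in either direction.
- Bias: none, if the loss is unrelated to exposure.

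**How likely is it that someone is open to exclusion?** The documents give no emesis rate. At assumed rates of 5 / 10 / 20% per subject within the window, the chance that at least one of 6 active subjects qualifies is 1 − (1 − p)⁶ = 0.27 / 0.47 / 0.74. This is the chance that the option arises, not that it is used.

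**The case against.** The strongest defence is that the rule forces nothing. The list says only what reasons may be. The sentence before it includes a parameter unless there is an important deviation relevant to the evaluation, and emesis is not a category in SAP Table 6.2: 1, although that table can be supplemented. A team that sees no relevance can keep every value. The sponsor's PK procedures, which cannot be seen, might also restrict emesis exclusions by route. This limits the impact. It does not make the item suitable for an injected drug, and a SAP is the place to settle the question in advance.

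The second defence is redaction. The abbreviations include "Auxiliary Medicinal Product", and Protocol 4.3 mentions "The measured plasma concentrations of investigational and non-investigational medicinal products", so a second product was apparently measured, and it may be oral. That could explain why emesis items are there at all. It stands for the second item: a labelled dosing interval has no visible meaning for BI 473494 in a single-dose first-in-human trial, so that item may concern the other product. A reader might call it an outright error, or say that the SAP leaves the analyte wholly unstated. Neither is supported, because explanatory text may have been removed and the PKS definition ties the list to BI 473494. The redaction argument does not clear the first item, whose window is set from the test product and which no visible text limits to another analyte.

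A reader might also infer that the reported exposure would be biased downward, since vomiting may go with high exposure. If the highest of 6 values were always the one lost, the expected log mean would fall by about 0.2537σ (simulated), a geometric mean of 0.93 / 0.91 / 0.89 of its true value at CV 30 / 40 / 50%. The documents do not establish any link between vomiting and exposure within a dose group, so this case carries no weight here.

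**Conclusion.** The point holds, and it is minor. For BI 473494, emesis at or before two times median tmax is not a sound reason to exclude AUC0-tz or Cmax, yet SAP 6.3 allows it. That vomiting cannot remove the dose follows from the route of administration; the documents do not state it.

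The consequences are small. SAP Section 4 restricts the analysis to the 35 and 75 µg groups, drops dose proportionality and makes the secondary endpoints descriptive only. Excluded subjects' concentrations and parameters are still listed, and the primary endpoint, subjects with drug-related adverse events, is not touched. Nothing in the documents shows that any subject vomited or that any value would be excluded. The percentages above rest on full groups of 6, assumed CVs and one assumed exclusion, so they are illustrations of size and not predictions.

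**What to change.** Add to SAP 6.3, directly after the list taken from the protocol: *Emesis alone is not a reason to exclude BI 473494 PK parameters, or to exclude a subject from the PKS, because BI 473494 is given subcutaneously; time deviations and restricted medications continue to apply.*

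If there is an orally given analyte, keep an emesis rule for that analyte only, and name it together with its window. This would also settle what the second item refers to. Record the departure from Protocol 7.3.2 in SAP Section 4.

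A subject who vomits and also takes a restricted medication is still assessed under that reason. The cost is a sentence or two in SAP 6.3 and one entry in Section 4, with no added data, staff or subjects.
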